### Intervention

It corresponds to "Task 2.2", WP2 in Table 1 (page 10). Every physiotherapy session lasts 30 minutes and it includes 20 minutes of exercise therapy based on 4 strengthening exercises and 10 minutes of manual therapy (focusing on the release of posterior capsule). The manual therapy will be applied to all the patients without distinction to the two groups. The exercise therapy will be the distinct element between the two groups: group 1 (G1, exercising into discomfort) will execute exercises with pain intensity from 4/10 to maximum 7/10 on a NPRS scale, while group 2 (G2, exercising with slight/no discomfort) will execute not/slightly-painful exercises with pain intensity inferior to 2/10. These limits are set in order to ensure a clear difference in pain intensity between the two groups and a preliminary analysis of the feasibility study showed it was possible for the patient in G1 to train between 4 and 7/10 following the high-pain monitoring model. The pain level in G1 will decrease to 0-2 at 9th week so the patients can focus on more proprioceptive or sport/work related tasks. The exercises are individually prescribed and each patient will have 4 personalized strengthening exercises, with one focusing on the painful direction (which is usually abduction, flexion or external rotation) and the rest of exercises will elicit pain but not in the painful direction (for example, closed kinetic chain exercises or exercises with elastic bands). The aim in both groups is to gain strength in both scapulothoracic and scapulohumeral muscles, re-balancing the force couples in the shoulder joint during specific movements (i.e. re-train arm elevation in which a lower activity of serratus anterior and overactivation of the upper trapezius is present), without isolating one muscle during the exercise. Scapula stabilization exercises will be integrated with rotator cuff strengthening in one exercise (i.e. closed kinetic chain as push-up) from the first session, since recent studies showed that the order of exercise (scapular and then RC exercises or vice versa) was not affecting significantly the clinical outcomes. Our hypothesis is that a painful shoulder program focusing on strengthening exercises, with certain caveats, will load the shoulder muscles allowing a better and possibly faster recovery.

The choice of the research team to not choose a particular and specific sets of exercises was motivated by two main reasons: 1) allow the physiotherapist to prescribe individualized exercises and 2) let the physiotherapist progress the exercise based on patient's needs (sport, work-related activities) and to adapt it on the load provoking pain. In both groups, lifestyle advice, ergonomics corrections, pain education regarding the subacromial shoulder pain will be provided, in line with current physiotherapy practice in Belgium^59. We believe that this approach of "exercising into discomfort" can give a different insight in the treatment of SSP but it will remain well-integrated in the current physiotherapy practice.

# Outcome measures

All outcomes will be measured at baseline (T0) and 6 (T1), 12 (T2), 26 (T3) weeks and the assessors will be blinded to group allocation. The **primary outcome** is the **difference in mean change between groups from T0 to T1, T2 (12 weeks, end of the treatment), and T3 (26 weeks, follow-up)** in the patient self-reported outcome score **Shoulder Pain and Disability Index (SPADI)**. This questionnaire is a patient-reported outcome measure (PROM) with high test–retest reliability and construct validity  and is available and validated in Dutch .

Secondary outcomes are registered for each patient at the same time points as the primary outcome, except for the Global Perceived Effect Score, which will be assessed after 1st treatment and then at 6 and 12 weeks. The secondary outcomes are:

**Scapular dyskinesis:** The procedure we will use is based on the procedures described by Tate et al.  and Struyf et al. . Scapular position will be observed at rest and during active loaded and unloaded humeral motion in a frontal and sagittal plane. The effect of scapular correction will be tested by means of the modified scapular assistance test and scapular retraction test . Reduction of pain during these tests compared with non-assistance during the same tests confirms scapular involvement in the shoulder complaints.

**Subacromial space**: Acromiohumeral distance (AHD) is a US measurement used to quantify the subacromial space. It is defined as the shortest linear distance between the most inferior aspect of the acromion and the humeral head . AHD is measured at 0 and 60 degrees of active shoulder elevation in the scapular plane, following the procedure of measurement indicated by Navarro-Ledesma et al . It has already been used to evaluate different populations, such as healthy volunteers  and patients with shoulder pain .

**Tendon changes**: Tendon structural changes (limited to RC thickness and long biceps) will be evaluated using US device and following international guidelines . STT will be also computed as percentage of subacromial space, known as the occupation ratio (using the formula [(STT/AHD)\*100] .

**Shoulder strength and Range of Motion (ROM)**: Shoulder strength is measured as isometric strength measurements with handheld dynamometer (IsoForce Dynometer EVO2; Medical Device Solutions AG) in abduction external rotation and scapular plane elevation. ROM in active and passive abduction and external/internal rotation will be determined with a goniometer (HALO digital goniometer; HALO, Medical Devices). These devices are already available at the University of Antwerp.

**Shoulder related Quality of Life**: Health-related Quality of Life index and Health-related Quality of Life VAS, measured with the EQ-5D-5L .

**Adherence:** The pain and the amount of exercise performed will be recorded in an exercise and pain diary. The participants will be asked to complete a pain diary, reporting pain on the VAS scale before and 1 hour and 1 day after each training session as well as the home training. Adherence will be analysed in terms of compliance with self-reported exercise diary: good compliance is defined by attendance of 6/9 supervised sessions and 80% of 27 home exercises.

**Fear of pain questionnaire-9 and Fear-Avoidance Beliefs Questionnaire (FABQ)**: these outcomes allow qualitative analysis of which patient characteristics (i.e. high level of anxiety and fear associated with pain) undermine compliance in case low adherence is observed. These questionnaires are both psychometrically sound and validated in Dutch.

**Other relevant outcomes**: Patients fill out the global perceived effectiveness (GPE) rating (1-much worse, 2-slightly worse, 3-no change, 4-slightly better, 5-much better) after the first session, at 6 and 12 weeks .

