# **Scientific Research Objectives**

The primary aim of this project is to provide proof-of-concept for the clinical effectiveness of the "exercising into discomfort" approach in patients with SSP. In the first three objectives, the focus will be on its effect on shoulder pain and functionality (patient-reported outcomes, objective 1), on scapular dyskinesis (objective 2), subacromial space, and the tendon structures (objective 3) during and after 3 months of exercise therapy in patients with SSP. In the fourth objective, the relationship between patient reported outcomes and the US measurements during the treatment course will be explored. Two groups will be compared in a randomized controlled trial (RCT): an intervention group "exercising into discomfort" (G1) and a control group "exercising without discomfort" (G2). The time points of assessment will be prior to the treatment at baseline (T0), at 6 weeks during treatment (T1), end of treatment at 12 weeks (T2), and follow up at 26 weeks (T3).

OBJECTIVE 1	To investigate the effectiveness of exercising into discomfort during a strength training program in the treatment of SSP on self-reported shoulder pain and function
Methods	Double Blind Randomized Controlled Trial comparing 2 groups (G1 versus G2), with SPADI (Shoulder Pain and Disability Index, a valid and reliable patient-reported outcome measure of pain and disability  ) as primary outcome. A "high pain monitoring model" will be used to monitor pain during and 1 hour after every exercise in G1 (see "intervention" in methodology).
Hypothesis	In G1 SPADI will be reduced more than in G2.
Novelty/ Relevance	If successful, the results of this study will lead to a reconceptualization of exercises in SSP, allowing pain (defined as discomfort sensation) to be an essential component and not a barrier in the physiotherapy treatment.

OBJECTIVE 2 ft	To investigate whether improvements in shoulder pain, function and quality of life is positively related with reduced presence of scapular dyskinesis
Methods	Scapular dyskinesis will be registered by visual observation at rest and during movements (abduction and flexion) and its effects on pain will be tested by scapular assistance test and scapular retraction test
Hypothesis	Scapular dyskinesis will decrease more in G1, in relation to the increase in strength and coordination of the scapulothoracic and scapulohumeral muscles.

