### Sample size

The sample size calculation was made using the Edland method, R package longpower 1.0-

11, based on the following data: 8% points as smallest clinically important difference in SPADI , 15% of estimated drop-out (as mean of dropout rates from previous studies ) and 30% for adjustment

for non-linearity of the data (since there is usually a higher decrease in SPADI in the first 3 months compared to 6 months). Considering a mixed regression model for repeated measures and using a moderate effect size (corresponding to 8% as smallest clinically relevant difference), confidence level at 5%, and power at 90%, the required total sample size is **54 subjects**, taking into account 15% dropout rate. The variance of the residuals cannot be estimated from previous studies, but it has a very limited effect on the sample size. It does not change the result of the power calculation, and therefore it is not included in this analysis.

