# WP3: Data analysis

Statistical analyses will be performed using JMP ®Pro 14.0.0 (SAS Institute Inc., Cary, NC, USA) . Level of significance is set at p= 0.05. Appropriate descriptive statistics will be performed.

**OBJECTIVE 1,2,3:** A mixed regression model for repeated measures will be used to assess both the evolution of SPADI (pain and function), strength, ROM and US parameters within persons from baseline (T0) over time (T1, T2, T3) and the differences in evolution between subjects. Potential confounders are: age, gender, BMI, previous corticosteroid injections, severity of initial symptoms. They will be measured during the history taking at the first assessment and added into the mixed regression model as co-variants. If for a certain variable the percentage of missingness will be more than 15%, multiple imputation for missed observation will be used. There are three assumptions for the mixed regression model: change over time, a sensible measure for time (multiple time points of measure), normality of residuals (it will be checked using a Shapiro-Wilk test). If these residuals are not normally distributed, an appropriate transformation will be performed first. Therefore, this model best fits the longitudinal design of the RCT. **OBJECTIVE 4**: correlation analysis between tendon structures and clinical symptoms using the correlation for pairs of continuous variables in JMP.

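### The primary SPADI outcome is three change contrasts at one 0.05 level, and the plan names no leading contrast, joint test, sequence or other rule for success

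*Combined protocol and SAP*

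**What the plan says.** The Outcome measures section (WP2) gives the primary outcome as the "difference in mean change between groups from T0 to T1, T2 (12 weeks, end of the treatment), and T3 (26 weeks, follow-up") in SPADI. The Objective 1 hypothesis, "In G1 SPADI will be reduced more than in G2", names no visit.

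WP3: Data analysis states "Level of significance is set at p= 0.05" and proposes a mixed regression model for repeated measures. The model is to describe SPADI "within persons from baseline (T0) over time (T1, T2, T3) and the differences in evolution between subjects". No group-by-time term, coding of time, contrast or order of testing is given, and sidedness is not stated. The covariates, taken from the history at the first assessment, are "age, gender, BMI, previous corticosteroid injections, severity of initial symptoms". On model checking: "If these residuals are not normally distributed, an appropriate transformation will be performed first".

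The Sample size section uses the Edland method, "Considering a mixed regression model for repeated measures and using a moderate effect size (corresponding to 8% as smallest clinically relevant difference"), and a 30% adjustment "for non-linearity of the data (since there is usually a higher decrease in SPADI in the first 3 months compared to 6 months"). It arrives at 54 patients for 90% power. The 2022 renewal (WP2: RCT) moves to 44 patients, 85% power and 10 points. It names neither a test nor a visit.

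**The concern.** SPADI is the only primary outcome, yet the rule that turns its data into a positive or negative trial is not written down. The plan leaves room for a test at any one visit, a joint test, an average over visits, or a slope. These answer different questions, need different numbers of patients and can disagree. Some hold the error at 5% and some do not. Unless the rule is fixed while allocation is blinded, it can be chosen after the results are seen, and neither a positive nor a negative claim could then be read with confidence.

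**Working it through.** **1. The plan's own figures.** The 54 cannot be rebuilt, because no SD, slope variance or within-person correlation is given. If a moderate effect means a standardised difference of 0.5 (an assumption), the SD is 8/0.5 = 16. A plain two-sample comparison then needs 2 × (1.960 + 1.282)² × 16²/8² = 84.1, so 85 per arm, or 170 in total before dropout. With repeated measures the total runs from 236 (change score, r = 0.3) to 40 (baseline-adjusted average of three visits, r = 0.8). The 54 therefore does not identify the test.

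Carrying 54 patients, 8 points and 90% over to 44 patients and 10 points on unchanged inputs gives (1.960 + 1.282)² × (44/54) × (10/8)² = 13.38. Power is Φ(√13.38 − 1.960) = Φ(1.70) = 95.5%, against the stated 85%. The gap can be closed by bookkeeping. If the 30% adjustment enters the 44 but not the 54, power is 89.4% (×1.3) or 86.4% (÷0.7). With the 15% dropout treated the same way as well, it is 84.9% (×1.3×1.15) or 84.1% (×1.3÷0.85). So how the 85% was obtained cannot be established, and neither power statement shows which test was meant.

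**2. Error rate if any visit counts.** The rate is 1 − P(|Z₁|, |Z₂| and |Z₃| all < 1.960), with the three contrasts trivariate normal. With equal visit correlations r, two changes from the same T0 have covariance 1 − r and variance 2(1 − r), so their correlation is 0.5 whatever r is.

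| Contrast correlation (assumed) | Any visit, two-sided | Any visit in favour of G1 |
|---|---|---|
| 0.3 | 13.6% | 6.8% |
| 0.5 | 12.5% | 6.3% |
| 0.7 | 10.9% | 5.5% |
| 0.9 | 8.4% | 4.2% |

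A single two-sided 5% test gives 5% and 2.5%. If visit correlations decay with time, the two-sided rate is 11.2% to 12.4%. A joint 3-df test holds 5%.

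**3. A slope is not the stated outcome.** For visits at weeks 0, 6, 12 and 26 the mean time is 11. The slope weights are −11, −5, +1 and +15, with sum of squares 121 + 25 + 1 + 225 = 372. With no expected difference at T0, the estimated gap at week 26 is 26 × (−5·d₁ + d₂ + 15·d₃)/372 for gaps d₁, d₂, d₃ at T1, T2, T3.
- Gaps 10/10/10: 26 × 110/372 = 7.7 points in favour of G1.
- Gaps 10/0/0: 26 × (−50)/372 = 3.5 points in favour of G2.

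An early gain thus counts against G1, although the Intervention section hopes for quicker recovery.

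**4. Baseline SPADI.** If T0 is a response and symptom severity enters only as a main effect, that covariate cancels from every change from T0. The result is valid but less precise. Per unit SPADI variance, a change score has variance 2(1 − r) and a baseline-adjusted one 1 − r². The ratio is (1 + r)/2, a reduction of (1 − r)/2: 35%, 25%, 15% and 10% at r = 0.3, 0.5, 0.7 and 0.8 (assumed).

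**The case against.** The strongest defence is that the outcome is written in the singular and one repeated-measures model is named for differences in evolution. On that reading a single group-by-time test is natural, and it holds 5%. This stands as a possible reading, but nothing in the plan commits to it, and neither the hypothesis nor the renewal supplies the missing rule.

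Four stronger readings are tempting and are not supported.
- A reader might infer that the plan has a 12.5% error rate. It does not adopt an any-visit rule; it only fails to exclude one.
- A reader might take 95.5% against 85% as proof that the test or an input was changed. Different handling of the plan's own 30% and 15% adjustments gives 84% to 89%. The combined case sits badly with the statement that 54 already allows for dropout, so it does not explain the 85% either.
- A reader might conclude that a linear slope is the planned analysis and will reverse the result. No linear time term is stated, and the slope is inferred from the sizing method. The reversal also needs an early gain that has gone by T3.
- A reader might think that the handling of baseline SPADI makes the analysis invalid. Since the covariates come from history taking, severity is probably not the T0 SPADI score, and T0 is probably a response. That analysis is valid; what is lost is precision.

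**Conclusion.** The point holds as a gap in the decision rule for the sole primary outcome: three contrasts, one level, and no leading contrast, joint test, sequence or success criterion. The inflation to about 12.5% (13.6% to 8.4%) is conditional on an any-visit rule and on assumed contrast correlations. The powered quantity is not tied to the stated outcome, because the sizing hints at a slope that would give T1 a negative weight. No shortfall against 85% is shown, since the documents give no SD or correlation. The 85% simply has no definite meaning until the test is named. Baseline adjustment is a matter of efficiency. The reporting scale after transformation and the T1 week are minor.

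**What to change.** Issue a dated amendment before the November 2022 unblinding given in the renewal. It should record that 42 patients had been recruited by the end of April 2022 and that allocation was still blinded.

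1. State one error-controlling rule, with visit as a categorical factor. Either name one test at two-sided 5% (a joint 3-df test over visits, one visit, or the T1–T3 average) and make the rest secondary, or use a fixed sequence or Holm procedure over the three contrasts. The choice is the sponsor's. Restate power at 44 patients for that rule, with its SD and correlation.
2. For efficiency, fit T1–T3 SPADI with T0 SPADI by visit as covariate, or keep T0 as a response with group means constrained equal there. In the first form a joint test must cover all three visit differences, because the 2-df group-by-visit interaction misses a constant benefit. Define initial symptom severity.
3. Minor: report the primary estimate in SPADI points even if a transformed model is fitted. Reconcile the T1 week, which is 9 in the renewal's Table 1 legend and 6 in the objectives, Design, Outcome measures and Work Plan sections.

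No new data are needed, and the T1–T3 form is a mixed model of the kind already named. Whether the named software fits the constrained-baseline form is not shown. With one named test, the other contrasts become secondary, which weakens the claim to faster recovery if T1 is among them. A fixed sequence stops at its first failure. Holm tests its smallest p-value at 0.05/3, so a contrast with 85% power at 0.05 is assured only Φ(1.960 + 1.036 − 2.394) = 73%.

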### Feasibility study

In the recruited private practice, the feasibility study is now ongoing (Task 1.3, WP1). It includes 12 patients, which will allow to test 80% of compliance rate, ranging between 0.78 and 0.84 within a 95% of confidence interval. This number was obtained with the "Score method incorporating continuity correction" reported by Newcombe et al. 

The feasibility study aims to: 1) test a high-pain monitoring model (which is the intervention applied in G1 -"exercise into discomfort"-) and the rate of adherence to this modality, 2) test the rate of recruitment at this private practice, 3) verify adverse effects 4) test the practicability of delivering clinical questionnaires via online survey Qualtrics, 5) provide an indication of the time needed to collect the data.

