The high pain monitoring model is based on the pain monitoring model which has been previously used in many studies. The difference is that the pain during exercise is higher than in the previous studies until the 9th week, with certain caveats: 1) during the exercises, the patient should feel discomfort/pain exceeding the pain at rest, ranging between 4 and 7 on NPRS (Numeric Pain Rating Scale). During the last set of 10/15 repetitions pain should not exceed 7; 2) Discomfort/pain should return to baseline level after 1 hour; 3) Discomfort/pain should not increase from day to day. In the last phase of the treatment (between 9th and 12th week) the pain during exercise ranges between 0 and 2 on NPRS, in order to allow the patient to focus on more proprioceptive and sport/work related tasks. A preliminary analysis of the data on 6 patients at the 6-week follow-up showed that all the subjects attended at least 4/6 physiotherapy sessions and they were all adherent to the home exercise (at least 10/11 home exercises completed) except one patient. Two patients experienced a slight increase (1 point on NPRS) in the level of pain after the physiotherapy or home exercise in the first three weeks. Discussing with both physiotherapists and patients, this was related to an increased level of sport in the same period or due to additional treatment of the posterior capsule, which can provoke initially some pain. The physiotherapist adapted the exercise and from the 4th week onwards the pain decreased to initial levels after 1 hour of exercise. Moreover, it emerged that a measurement of the pain after 1day was necessary to evaluate the evolution of the pain after painful exercises. This will be added in the design of the RCT and it is also in line with the recent recommendation for evaluating pain during and after exercises.

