Feasibility study and fine-tune the protocol (WP1, 1.3 1.5): Aim: a feasibility study on exercise into discomfort was performed from November 2019 to May 2020. Status: completed (start delayed compared to FWO initial project, from Q3-2019 to Q4-2019). A critical revision of the protocol for the RCT was performed after the feasibility study, as mentioned in the FWO application. Some changes were necessary to the protocol. 1) Changes to the intervention in the RCT: the intervention in the RCT changed from 4 exercises into discomfort between 4-7 on a Numeric Pain Rating Scale (NPRS, scale 0-10) proposed in the initial FWO application to 1 exercise into discomfort and the 3 remaining exercises performed with no/minimal pain. This modification was necessary after a thorough analysis of the feasibility study and discussion with the physiotherapists and the research team. If this single painful exercise was not provocative anymore (4-7 on NPRS) before 9 weeks, a rate of perceived exertion (Borg Scale) was used instead of the NPRS. In this way, the exercises could be between 4 (somewhat hard) and 7 (very hard) representing more the subjective effort during the exercise than the pain provoked during the exercises. Although this modification could potentially change the comparison between a painful vs. non-painful exercise program, this final decision was taken together with the research team in order to compensate possible deviations from the protocol in the future RCT. 2) Impact of Covid-19 on feasibility study: patients stopped to go to the physiotherapists from March to May 2020 but they continued to exercise at home. Questionnaire were sent online via Qualtrics, therefore subjective data were not lost. Objective measures (i.e. strength and US measures) were lost for 7 patients at follow-up of 6 and/or 12 weeks but available data for patients who went at least 7 out of 9 sessions to the physiotherapists were analysed in order to adjust the protocol for the RCT. Milestone 1 (ethical approval on amendments to the protocol and fine-tune the protocol for the RCT): completed according to the plan.

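### The RCT names no harms outcome and plans no analysis of the diary pain readings, so post-session flare-ups and adverse events would not be compared between groups

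*Combined protocol and SAP*

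**What the plan says.** **Harms.** Adverse effects appear once, as an aim of the feasibility study: "verify adverse effects". That study has 12 patients, tests the G1 intervention, and describes no comparison group. Outcome measures (WP2) lists SPADI, scapular dyskinesis, acromiohumeral distance, tendon measures, strength, range of motion, EQ-5D-5L, adherence, two fear questionnaires and global perceived effect (GPE). No adverse-event, flare-up or other harms outcome is among them. The 2022 renewal adds none.

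**Diary.** Under Adherence, participants keep a diary "reporting pain on the VAS scale before and 1 hour and 1 day after each training session as well as the home training". The one analysis stated is "Adherence will be analysed in terms of compliance with self-reported exercise diary", with good compliance set at 6 of 9 supervised sessions and 80% of 27 home exercises. WP3: Data analysis puts SPADI, strength, range of motion and ultrasound parameters into the mixed model and does not mention diary pain.

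**Limits on pain.** The Feasibility study section attaches conditions to the high-pain model: "2) Discomfort/pain should return to baseline level after 1 hour; 3) Discomfort/pain should not increase from day to day". It adds that the 1-day reading proved necessary for following pain after painful exercise and would go into the RCT.

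**Exposure.** The Intervention section says "group 1 (G1, exercising into discomfort) will execute exercises with pain intensity from 4/10 to maximum 7/10 on a NPRS scale". The renewal (WP1: Preparation of the trial) instead describes "1 exercise into discomfort and the 3 remaining exercises performed with no/minimal pain", with a Borg effort rating if that exercise stops provoking pain before 9 weeks.

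**The concern.** Pain during exercise is the experimental factor, and the rationale is that such pain is not harmful. The RCT is the only stage with a comparison group, so it is the only stage that can test that premise. The plan sets its own limits on post-exercise pain and collects readings that bear on them, but does not define a breach as an outcome or compare breaches between groups. A SPADI advantage for G1 could then be reported with no prespecified account of what patients went through, session by session, to obtain it. Flare-up definitions chosen after unblinding would carry much less weight.

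**Working it through.** The plan gives no figure for harms, so there is nothing to reproduce. The check compares the sections, then asks what an added analysis could deliver.

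**1. What each planned element can show**

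| Element | When | Named in WP3? | Can show |
|---|---|---|---|
| SPADI | T0, 6, 12, 26 weeks | Yes | Lasting worsening of pain and function |
| GPE, ratings 1–2 | After first session, 6, 12 weeks | No | Patient-rated worsening, to 12 weeks |
| Diary pain | Before, 1 hour and 1 day after sessions | No (compliance only, under Adherence) | Post-session flare-ups |
| Adverse events, withdrawals for pain | Not described | No | – |

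The last two rows are the gap.

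**2. Volume of diary data**

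- Sessions per patient: 9 supervised + 27 home = 36, which agrees with 12 weeks × 3 per week = 36 (Design).
- Post-session readings per patient: 36 × 2 = 72. For 44 patients: 72 × 44 = 3,168.
- Session records per group, assuming equal allocation (44 / 2 = 22): 22 × 36 = 792.

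These records are clustered within patients. With within-patient correlation ρ, the effective number is 792 / (1 + 35ρ): 792 at ρ = 0 and 792 / 36 = 22 at ρ = 1. The documents give no ρ. Intervals that treat sessions as independent would be too narrow.

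**3. Precision when no patient in a group has the event**

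The upper limit is 1 − α^(1/n).

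- n = 22, one-sided 95%: 1 − 0.05^(1/22) = 12.7%.
- n = 22, two-sided 95%: 1 − 0.025^(1/22) = 15.4%.
- n = 18 (22 × 0.85 = 18.7, rounded down, for 15% dropout): 15.3% and 18.5%.

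The chance of seeing at least one event in 22 patients is 1 − (1 − p)^22: 68% if p = 5%, 90% if p = 10%.

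**4. Would a significance test help?**

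For two proportions with n per group and two-sided 5%, power = Φ{[|p1 − p2| − 1.96√(2p̄(1 − p̄)/n)] / √[(p1(1 − p1) + p2(1 − p2))/n]}. The flare-up proportions below are assumptions for illustration, with n = 22.

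- 33% v 10%: 46%
- 33% v 5%: 67%
- 50% v 10%: 85%

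Only a large contrast would be detected reliably, and a non-significant result could be misread as evidence of safety.

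**5. Can the feasibility data stand in?**

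The report is "Two patients experienced a slight increase (1 point on NPRS) in the level of pain after the physiotherapy or home exercise", from a preliminary analysis of 6 patients. 2/6 = 33%, exact (Clopper–Pearson) 95% interval 4.3% to 77.7%. The interval is too wide to be useful, and there is no comparison group.

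**The case against.** The strongest reply is that harm is not invisible in this trial. SPADI measures pain and disability and is compared between groups to 26 weeks. GPE has two categories for worsening, and strength, range of motion, tendon thickness and EQ-5D-5L are also collected. That stands. A reader might infer that net benefit and safety could not be judged at all, but the documents do not support this, because lasting deterioration would be seen. What these measures miss is short-lived flare-ups between visits and discrete adverse events.

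Three other tempting readings also go too far.

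- **That the diary exists only for adherence.** The Feasibility study section gives the 1-day reading a pain-related purpose, and WP3 promises descriptive statistics in general terms. The fair statement is that this purpose has no specified analysis.
- **That one third of G1 patients can be expected to flare up.** The rise in those two patients was 1 point, occurred in the first three weeks and had settled from week 4. It was attributed to extra sport or to posterior-capsule treatment, which the RCT gives to both groups. It also predates the renewal's change to one painful exercise. It does not estimate G1 harm in the current RCT.
- **That everything needed is already in hand for both groups.** Outcome measures speaks of participants without restriction, but Objective 1 describes pain monitoring during and 1 hour after exercise for G1. The limits are stated for the G1 model on the NPRS, while the diary uses a VAS. No section describes collecting injections, surgery or other events up to T3, and the diary follows training sessions, which end at 12 weeks.

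**Conclusion.** The point holds as an omission. No harms outcome is named for the RCT, and WP3 leaves the diary pain readings without analysis, although the plan states why the 1-day reading matters and sets limits on post-exercise pain. Followed as written, the trial would compare lasting worsening through SPADI but not post-session flare-ups or adverse events. The smaller G1 exposure in the renewal narrows the stakes but does not close the gap.

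An added analysis would be descriptive. At 22 per group it could not exclude a true event rate of up to 12.7% (one-sided 95%) or 15.4% (two-sided 95%) when no events are seen. This assumes equal allocation, 44 patients and complete follow-up. A flare-up comparison also assumes that G2 completes the diary, which the documents leave open.

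**What to change.** The renewal keeps allocation blinded until November 2022. Before unblinding, add a harms outcome to Outcome measures and its analysis to WP3:

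- **Flare-ups, by group.** Number and proportion of patients with pain above the pre-session level at 1 hour, and separately at 1 day, using a rise on the diary VAS fixed in advance so that measurement noise is not counted. Give the between-group difference with a confidence interval, and the number of completed diary records per group.
- **Session-level rates** only from a method that allows for repeated sessions per patient: mixed model, GEE or patient-level bootstrap.
- **Events, by group.** List recorded withdrawals because of pain and recorded adverse events. State that injections, surgery and other events up to T3 are not described as collected.
- **Presentation.** Counts and intervals beside SPADI, with no significance test. Do not use the 2/6 feasibility result as an estimate of G1 harm.
- **Clarify first.** Confirm that G2 completes the diary. Reconcile the Intervention section with the renewal on the G1 exposure, so that the reported harms refer to a defined intervention.

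The cost is an outcome paragraph, a short analysis paragraph, one table and diary coding time. Precision for rare events stays low. With 42 patients recruited by the end of April 2022, any event data not already recorded may have to be recovered retrospectively or reported as unavailable. Treatment and sample size do not change.
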